## 7.7 Emergency situations

Given participation is completely virtual, for any potential emergency situation that occurs while on the phone with participants, the study staff will ask the participant to call 911 or their physician as needed. Permission will be obtained at study outset (consent) to contact an emergency contact as needed. The study physician and key staff will also be informed ASAP, and an AE form will be recorded. (Emergency numbers are listed in TEAMS.)

## **8 INTERVENTION DISCONTINUATION**

### **8.1 Discontinuation of Intervention for a Participant**

Participants will be discontinued if adverse events cause:

- Cognitive impairment that prevents participant's understanding or ability to comply with study requirements; or
- Emotional distress that results in psychosis or hospitalization for psychological trauma.

In these situations, study staff will continue to follow-up until participants are under the care of their provider.

Participants may voluntarily withdraw their participation in the study at any time and for any reason. We anticipate that the family care team may wish to withdraw at the time of the death of the care recipient. Participants will continue to be followed, with their permission, even if withdrawal occurs prior to all study activities being completed. All participants that withdraw early, but continue to be followed, will receive follow-up calls to complete the *Telephone Administered Adverse Event Monitoring Form*. Participants will be asked to complete the *Final Evaluation* for the study (see [Section 6.1.4](#)) at the same time point of those in their cohort. If participants withdraws prior to completing all study activities and refuses to be followed, they will be instructed to connect with their primary care provider for any unresolved adverse events and asked to complete the *Final Evaluation* for the study (see [Section 6.1.4](#)) at the time of withdrawing from the study.

If the withdrawal rate is higher than anticipated (see [Section 9.3](#)), additional cohorts may be recruited to reach an adequate sample size.

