#### **Design and Outcomes**

The proposed study utilizes a single-group, uncontrolled design to assess the feasibility and acceptability of telephone-delivered mindfulness training designed to alleviate caregiver burden for rural caregivers of African American individuals with moderate to severe dementia. A care partner—the person who provides the most support in addition to the primary caregiver—is included in the intervention. The primary outcome is feasibility as assessed by an 85% retention rate with completion of at least 6 of the intervention sessions. Pre- and post-participation interviews will assess acceptability.

At baseline, after obtaining informed consent, study staff will interview primary caregivers in their homes (or via a phone call post-COVID) and will administer a set of questionnaires, including the 12-item Zarit Burden Interview as well as measures of:

- 1) family satisfaction;
- 2) tolerance of uncertainty;
- 3) cognitive emotion regulation;
- 4) general self-efficacy;
- 5) anxiety and anger;
- 6) self-efficacy in managing emotions;
- 7) global physical health;
- 8) family conflict;
- 9) social support (emotional, instrumental, informational);

*10) meaning and purpose;*

*11) cognitive and affective mindfulness*

Study staff will interview the care partner in person or over the telephone. After the 8-week intervention, study staff will interview the caregiver (in the home, or via telephone), care partners (on the telephone) once more, and administer the questionnaires.

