#### 6.1.2. Enrollment, Baseline, and/or Randomization

##### Enrollment

The first enrollment date is defined as the date that the primary caregiver reviews and signs the written informed consent document. A primary caregiver may still choose to withdraw from the intervention prior to the first intervention session. The primary caregiver will become ineligible for the first intervention session if a care partner does not agree to participate. Hence, a second definition of enrollment, akin to the point of randomization, is the date of the first intervention session. Each individual who participates in the first class session will be considered to be a participant in the intervention. The date of enrollment (baseline assessment) and attendance at the first class session are recorded in the secure study database, REDCap.

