## 9.2 Sample Size and Randomization

We calculated the effect size for the feasibility outcome, the acceptability outcome, and the Zarit Burden Interview. The sample size depends on the number of individuals who can reasonably participate in a telephone mindfulness intervention and takes into consideration the challenges of recruiting study participants in rural areas among underprivileged groups. We expect that no more than 8 caregivers could participate in a call at one time. Limiting the group size to 8 will ensure that all participants have an opportunity to contribute and that the instructor can keep track of all participants.

We anticipate being able to recruit no more than 36 CG-CP dyads in two years and expect a withdrawal rate of 10-15%. We anticipate having 32 dyads join the intervention and complete all baseline assessments and that 28 of those will complete all post-participation assessments. We will make every effort to follow-up with every participant, either in person or on the telephone, resulting in little missing qualitative data. We will use multiple imputation procedures to account for missing quantitative data.

Based on a sample size of 32 and a pre-post correlation of 0.5-0.7, we will have 75-80% power to detect a pre-post difference in the ZBI means of 3.3 – 4.2 consistent with an effect size of about 0.5 utilizing and alpha of 0.05. This effect size is consistent with those reported in other mindfulness interventions. The sample size of 32 with a feasibility of 85% would result in a 95% CI of 72.5 to 97.5. Similarly, a sample size of 32 with an acceptability of 85% (based on interviews with participants) will result in a 95% CI of 72.5 to 97.5. If we have higher than anticipated withdrawal rates, we will have lower precision.

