## 9.3 Interim analyses and Stopping Rules

We do not plan an interim analysis. The study will be stopped if 3 or more individuals have a serious adverse event probably or definitely related to the study.

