## 9.4 Outcomes

### 9.4.2 Primary outcome

- 1) The primary outcome is feasibility. We define feasibility as 85% of participants who start the intervention will complete at least 6 of the intervention sessions. Feasibility is measured by class session attendance records collected at the time of the calls by the instructor. The instructor will notify the project manager who attended the call and the project manager will document attendance in the REDCap database.
- 2) (Qualitative) A second primary outcome is acceptability. We define acceptability as 85% of participants expressing comfort with the majority of the intervention components and homework.

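### Section 8.1 lets cohorts be added when withdrawal is high, and the plan does not say that the primary feasibility rate stays with the first 32 dyads

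*Combined protocol and SAP*

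**What the plan says.** Section 8.1 opens the extension with the condition "If the withdrawal rate is higher than anticipated", points to Section 9.3 for the anticipated rate, and continues: "additional cohorts may be recruited to reach an adequate sample size". It gives no limit on the number of added cohorts, no time at which withdrawal is judged, and no rule on how the added participants enter the analysis.

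Section 9.3 contains no withdrawal rate. Section 9.2 does: the investigators "expect a withdrawal rate of 10-15" per cent. Section 9.2 also describes what high withdrawal would mean: "If we have higher than anticipated withdrawal rates, we will have lower precision". Section 9.3 states: "We do not plan an interim analysis".

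The Précis, under Design and Outcomes, puts the primary outcome in terms of retention: "The primary outcome is feasibility as assessed by an 85% retention rate with completion of at least 6 of the intervention sessions". Section 9.4.2 gives the working definition: "We define feasibility as 85% of participants who start the intervention will complete at least 6 of the intervention sessions". The Enrollment text in Section 6.1.2 says who counts as having started: "Each individual who participates in the first class session will be considered to be a participant in the intervention".

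**The concern.** Withdrawal above 15% is nearly the mirror image of retention below 85%. A decision to add cohorts because of withdrawal is therefore likely to be taken when the feasibility result is running below its target. The denominator in Section 9.4.2 is everyone who starts, so on a plain reading the added starters enter the feasibility rate.

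The size of the feasibility sample could then depend on data closely related to the primary outcome. A result just short of 85% could be lifted over the line by a good extra cohort, while a result already at 85% would face no such second reading. The chance of declaring feasibility when true completion is below 85% goes up, and the interval quoted in Section 9.2 for a sample of 32 no longer describes the procedure actually followed.

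**Working it through.** **Inputs.** 32 dyads start, and no more than 36 are expected to be recruited in two years (Section 9.2). Groups hold up to four dyads, that is eight people (Section 2.2), and eight cohorts are planned (Section 7.6). The criterion is 85% (Section 9.4.2). The true completion rates of 80% and 75% are assumptions chosen for illustration.

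**Check of the plan's own figure.** 0.85 ± 1.96 × √(0.85 × 0.15 / 32) = 0.85 ± 0.124, or 72.6% to 97.4%. This agrees with the stated 72.5 to 97.5 within 0.1 point.

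**Pass marks.** The mark is the smallest whole number at or above 0.85 × n.
- 32 dyads: 27.2, so 28 are needed (27/32 = 84.4% fails).
- 36 dyads: 30.6, so 31.
- 64 individuals: 54.4, so 55.
- 72 individuals: 61.2, so 62.

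**Dyads, true rate 80%, independent outcomes.**
1. Fixed at 32: P(X ≥ 28) = 20.4%.
2. One cohort of four added after a fail, all starters pooled. From 27/32, all 4 new dyads must complete. From 26/32, 5 of 4 would be needed, which is impossible. So only 27/32 can be rescued: P(X = 27) × 0.80⁴ = 0.1558 × 0.4096 = 0.0638.
3. Total: 0.2044 + 0.0638 = 26.8%.
4. A design fixed at 36 from the outset: P(X ≥ 31) = 24.6%. The part due to extending only after a fail is 26.8 − 24.6 = 2.2 points. The rest comes from the larger sample and from where the rounded pass mark falls.

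**Dyads, true rate 75%.** Fixed at 32: 7.0%. With one added cohort: 0.0698 + 0.0832 × 0.75⁴ (0.3164) = 9.6%. Fixed at 36: 8.3%. The conditional part is about 1.3 points.

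**Individuals, true rate 80%.** Fixed at 64: P(X ≥ 55) = 15.0%. With one added cohort of eight, only 54/64 can be rescued, and it needs 8 of 8: 0.0907 × 0.1678 = 0.0152. Total: 0.1504 + 0.0152 = 16.6%. Here a design fixed at 72 would pass only 12.3% of the time (62 or more of 72). The split between sample size and conditional extension therefore depends on the rounding of the pass mark. The rise over the planned sample is the steadier measure.

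**The case against.** Five points on the other side deserve weight.

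- The extension is optional and its stated purpose is sample size. A reader might infer that a failing feasibility result automatically brings a retest. The documents do not say so: no section provides for retesting feasibility or for dropping early cohorts. This stands.
- Withdrawal only approximates failing the criterion. Someone can remain in the study with fewer than six sessions, or leave after the sixth. The anticipated rate could also refer to loss before the first session (36 recruited to 32 joining, 4/36 = 11.1%) rather than afterwards (32 to 28, 4/32 = 12.5%). Loss before the start is outside the feasibility denominator. This stands, although the Précis itself calls the outcome retention.
- Pooling keeps every early failure, so extra cohorts dilute a poor result and do not replace it. With two added cohorts, 27/32 needs 7 of 8 and 26/32 needs 8 of 8; 25/32 or fewer cannot be rescued. This stands and limits the effect to near misses.
- A reader might see Sections 9.2 and 9.3 as contradicting 8.1. They are in tension with it, but lower precision is a consequence and added cohorts an optional mitigation, so both can be true. Counting withdrawals in an open single-arm study is not necessarily an interim analysis.
- A reader might also quote two added cohorts, which give 31.2% at a true rate of 80% (32.4% if the rate is read after each). That needs 40 dyads, above the plan's ceiling of 36, and a fixed design of 40 would already pass 28.6% of the time.

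None of this settles which participants form the feasibility set once cohorts are added. That gap remains, as does the wrong cross-reference.

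**Conclusion.** The concern holds in a limited form. As written, the plan lets recruitment continue on the strength of data close to the primary outcome and counts the added starters in the feasibility rate. This modestly raises the chance of reaching 85% after a near miss: at a true rate of 80%, by 6.4 points counting dyads (20.4% to 26.8%) or by about 1.5 points counting individuals (15.0% to 16.6%).

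The figures assume independent outcomes, a decision on the observed proportion alone, an extension after every fail, one full added cohort, withdrawal standing in for failure to complete six sessions, and added cohorts with the same true rate as the first 32 dyads. Reaching 36 starting dyads would also need every recruited dyad to start. Since the extension is optional, the real gain could be smaller. Correlation within dyads or cohorts would change the numbers.

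The reference to Section 9.3 for the anticipated withdrawal rate is an error whatever view is taken of the rest.

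**What to change.** - In Sections 8.1 and 9.4, state that the feasibility verdict is based on the first 32 dyads to start the intervention. Counting dyads is safer than counting cohorts, because groups may hold fewer than four.
- State that cohorts added because of withdrawal serve the exploratory Aim 2 analyses, and that completion is also reported for all starters, with and without those cohorts.
- Align 8.1 with the statement in 9.2 that high withdrawal means lower precision, so that the plan gives one account of what happens.
- Correct the cross-reference in 8.1 from 9.3 to 9.2.

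This changes wording only. The cost is that attendance in added cohorts does not count toward the primary verdict, though it is still reported.

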## **9 STATISTICAL CONSIDERATIONS**

### **9.1 General Design Issues**

Hypotheses related to the study are provided in this protocol. A single-arm, pre-post design will assess the primary outcomes of feasibility and acceptability. Eight weekly intervention sessions with a retreat is considered the minimum amount of time needed to deliver all components of the intervention. Please see Table 3 for reliability and validity information for each of the scales.

**SPECIFIC AIM 1:** To determine the feasibility and acceptability of a telephone-delivered mindfulness training intervention (TMT) in decreasing caregiver burden among rural, African American, informal caregiving teams of people with dementia.

**Hypothesis 1:** TMT will be feasible within the rural, African American, informal caregiving teams. Feasibility is established when 85% (95% CI: 72.5, 97.5) of participants in the telephone-delivered mindfulness training intervention complete at least six sessions of the intervention.

Hypothesis 2: The adapted TMT will be acceptable to rural, African American, informal caregiving teams as evidenced by an 85% (95% CI: 72.5, 97.5) endorsement of the program in post-participation interviews.

SPECIFIC AIM 2: To explore, on a preliminary basis, the effects of the training on caregiver burden and relevant secondary outcomes for both caregiving team members, including:

SPECIFIC AIM 2: To explore, on a preliminary basis, the effects of the training on caregiver burden and relevant secondary outcomes for both caregiving team members, including:

Hypothesis 1: Compared with baseline levels, we hypothesize that mindfulness training will reduce caregiver burden (Zarit Burden Interview).

Hypothesis 2: Compared with baseline levels, we hypothesize that mindfulness training will improve emotion regulation by increasing positive coping styles (acceptance, positive refocusing, positive reappraisal) and decreasing negative coping styles (rumination, catastrophizing, self-blame) as measured by the Cognitive Emotion Regulation Questionnaire.

Hypothesis 3: Compared with baseline levels, we hypothesize that mindfulness training will increase tolerance of uncertainty as measured by (an adapted form of) the Intolerance of Uncertainty Scale.

Hypothesis 4: Compared with baseline levels, we hypothesize that training in mindful communication will increase perceived social support among the caregivers (PROMIS Social Support short forms).

Hypothesis 5: Compared with baseline levels, we hypothesize that training in mindful communication reduce family conflict around caregiving (Family Conflict Scale).

Hypothesis 6: Compared with baseline levels, we hypothesize that mindfulness training will reduce anger and anxiety (PROMIS scales).

Hypothesis 7: Compared with baseline levels, we hypothesize that mindfulness training increase global self-perceived physical health (PROMIS short forms).

Hypothesis 8: Compared with baseline levels, we hypothesize that mindfulness training increase meaning and purpose (PROMIS short form).

Hypothesis 9: Compared with baseline levels, we hypothesize that mindfulness training along with a caregiver resources handbook will increase caregiver general and emotional self-efficacy (PROMIS scales).

Hypothesis 10: Compared with baseline levels, we hypothesize that mindfulness training will increase family satisfaction (Family Satisfaction Scale).

Hypothesis 11: Compared with baseline levels, we hypothesize that mindfulness training will increase mindfulness (Cognitive and Affective Mindfulness Scale).

SPECIFIC AIM 3: To explore comfort with and willingness to adopt technologies (e.g. telephone-based, web-based) to access mindfulness practices and existing caregiving educational resources. As part of intervention planning, using interviews, we will investigate comfort with a smartphone/tablet. For half of the groups of participants, we will provide a tablet loaded with the handbook and all of the intervention materials. In this way we can compare engagement and program acceptability rates between groups who received the tablets and those who did not.

## 9.2 Sample Size and Randomization

We calculated the effect size for the feasibility outcome, the acceptability outcome, and the Zarit Burden Interview. The sample size depends on the number of individuals who can reasonably participate in a telephone mindfulness intervention and takes into consideration the challenges of recruiting study participants in rural areas among underprivileged groups. We expect that no more than 8 caregivers could participate in a call at one time. Limiting the group size to 8 will ensure that all participants have an opportunity to contribute and that the instructor can keep track of all participants.

We anticipate being able to recruit no more than 36 CG-CP dyads in two years and expect a withdrawal rate of 10-15%. We anticipate having 32 dyads join the intervention and complete all baseline assessments and that 28 of those will complete all post-participation assessments. We will make every effort to follow-up with every participant, either in person or on the telephone, resulting in little missing qualitative data. We will use multiple imputation procedures to account for missing quantitative data.

Based on a sample size of 32 and a pre-post correlation of 0.5-0.7, we will have 75-80% power to detect a pre-post difference in the ZBI means of 3.3 – 4.2 consistent with an effect size of about 0.5 utilizing and alpha of 0.05. This effect size is consistent with those reported in other mindfulness interventions. The sample size of 32 with a feasibility of 85% would result in a 95% CI of 72.5 to 97.5. Similarly, a sample size of 32 with an acceptability of 85% (based on interviews with participants) will result in a 95% CI of 72.5 to 97.5. If we have higher than anticipated withdrawal rates, we will have lower precision.

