#### 6.1.4. Completion/Final Evaluation

Study staff will make an appointment with the primary caregiver to complete assessments within 4 weeks of the last telephone class session, regardless of how many sessions the caregiver attended. With the research assistant, the caregiver will complete the following assessments:

- Post-participation interviews will address the caregiver's attitudes and experiences with the program, including:
  - most memorable aspects of program;
  - perceived value and cultural congruence of the mindfulness training;

- usefulness, challenges, and recommended changes;
- perceived value for management of stress related to caregiving or family conflict;
- tools that might help maintain practices;
- unfulfilled expectations of the program;
- usefulness of the technology components (e.g., call-in lines, tablets), if relevant.

Study staff will complete a similar interview with the care partner over the telephone. With permission of the participants, each interview will be audio-recorded and transcribed.

- Questionnaires to be completed with the caregiver and care partner at the final visit include all previously administered outcome measures.

If participants withdraw before the end of the intervention, study staff will ask them to complete the interview and questionnaires associated with the final visit, if possible, either in person or over the telephone. Study staff will also inquire about adverse events that may have led to discontinuation.

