## 9.5 Data Analyses

This is a single-arm pilot feasibility study with one baseline and one post-intervention measure.

Quantitative variables

For all quantitative questionnaire measures (outcomes 3-11), the change in the measure from baseline to post-participation is the outcome. First, we will examine variable distributions and missing data patterns. Next, we will conduct exploratory, descriptive analyses to assess *patterns of change* associated with participation in the programs for each of the variables including proximal mediating outcomes, intermediate outcomes (secondary stressors), and distal health outcomes. Because all analyses are exploratory, we will next perform bivariate assessments utilizing a paired t-test, analyzing caregivers and care partners separately. We do

not plan to adjust for multiple comparisons, but will interpret results conservatively and with great caution.

We will also explore the use of multivariable methods to enable us to control for variables that could influence the outcomes. Adjusted models will utilize repeated measures mixed models with individuals nested in families as random effects. We will control for the baseline FAST score (severity of dementia) and the relationship to the care recipient (spouse, adult child, other relative). In this small study (32 dyads), it will not be possible to formerly assess subgroups defined by gender. However, we will produce descriptive statistics by gender and age group.

We plan to invoke an intention-to-treat analysis in dealing with missing data using multiple imputation or full information maximum likelihood methods.

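### Section 9.2 quotes 75–80% power for the Zarit Burden Interview on 32 pre-post pairs but expects only 28 of 32 dyads to complete; at 28 pairs power is about 72%

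*Combined protocol and SAP*

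**What the plan says.** Section 9.2 gives the plan's only power figure: "Based on a sample size of 32 and a pre-post correlation of 0.5-0.7, we will have 75-80% power to detect" a mean ZBI difference of 3.3 to 4.2 points, described as an effect size of about 0.5 at alpha 0.05. The SD of the ZBI and the sidedness of the test are not given.

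The preceding paragraph of the same section expects 32 dyads to join and complete baseline, and that "28 of those will complete all post-participation assessments". It puts withdrawal at 10–15% and says that missing quantitative data will be multiply imputed. The only caution about loss is conditional: "If we have higher than anticipated withdrawal rates, we will have lower precision".

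Section 9.5 describes the analysis as "bivariate assessments utilizing a paired t-test, analyzing caregivers and care partners separately", and proposes "dealing with missing data using multiple imputation or full information maximum likelihood methods". Section 6.1.4 schedules the caregiver's final assessment "within 4 weeks of the last telephone class session, regardless of how many sessions the caregiver attended".

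**The concern.** A paired t-test uses only people with both a baseline and a follow-up value. Section 9.2 expects to lose 4 of 32 dyads (12.5%, inside its own 10–15%) yet computes power as if all 32 supplied a pair. Its warning covers withdrawal beyond the expected level, so the loss already expected is treated as having no cost.

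At stake is whether the stated power is what the design delivers under its own assumptions. A reader who relies on 75–80% would overestimate the chance of detecting a change in burden, which is the first hypothesis under Aim 2.

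**Working it through.** **Inputs.** From Section 9.2: n = 32 for the power statement, 28 complete dyads expected, effect size about 0.5, pre-post correlation r = 0.5–0.7, alpha 0.05. From Section 9.5: paired t-test, caregivers and care partners separately. Assumed: a two-sided test.

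**Which effect size.** The change has SD = SD(raw) × √(2(1 − r)). Between r = 0.7 and r = 0.5 that multiplier has ratio √(0.6/1.0) = 0.77. The ratio of the stated differences is 3.3/4.2 = 0.79. So 0.5 behaves as mean change divided by SD of change (d). The implied raw SD is 4.2/0.5 = 8.4 at r = 0.5, and 3.3/0.5/0.775 = 8.5 at r = 0.7. Reading 0.5 as a raw-SD effect instead gives 94.3% power at r = 0.7 with 32 pairs, which does not match the plan.

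**Formula.** Power = P(|T| > t(0.975, n − 1)), where T is noncentral t with n − 1 degrees of freedom and noncentrality d√n.

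**Reproducing the plan.** With n = 32 and d = 0.5, the noncentrality is 0.5 × √32 = 2.83 and power is 78.2%, inside the stated 75–80%. A one-sided 0.05 test would give 86.9%, which is outside it. This supports the two-sided reading.

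**Power for fewer pairs (two-sided 0.05).** The last two columns use the effect sizes that give exactly 75% and 80% at 32 pairs.

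| Caregiver pairs | Power at d = 0.5 | Power at d = 0.481 | Power at d = 0.511 |
|---|---|---|---|
| 32 | 78.2% | 75% | 80% |
| 31 | 76.8% | | |
| 30 | 75.4% | 72.1% | 77.2% |
| 29 | 73.9% | | |
| 28 | 72.3% | 68.9% | 74.2% |

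At 28 pairs the whole quoted range falls below 75%.

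**Detectable effect at 80% power.** d = 0.511 with 32 pairs, 0.529 with 30 and 0.549 with 28. With the implied SD of 8.4, 28 pairs correspond to 0.549 × 8.4 × 0.775 = 3.6 points at r = 0.7 and 0.549 × 8.4 = 4.6 points at r = 0.5.

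**What imputation recovers.** Suppose 4 of 32 follow-up values are missing and the baseline ZBI is the predictor. The variance of the mean change is then proportional to (1 − r²)/28 + (1 − r)²/32, against 2(1 − r)/n for n complete pairs. The effective number of pairs is 2(1 − r) / [(1 − r²)/28 + (1 − r)²/32]:

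- r = 0.5: 1.0 / (0.75/28 + 0.25/32) = 28.9 pairs, power 73.7%
- r = 0.7: 0.6 / (0.51/28 + 0.09/32) = 28.5 pairs, power 73.1%

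A simulation of multiple imputation (20 imputations, Rubin's rules with small-sample degrees of freedom, 20,000 runs, d = 0.5) gave 72.3% at r = 0.5 and 71.8% at r = 0.7 with 28 of 32 observed. With 30 of 32 observed it gave 75.2% and 74.8%.

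**The case against.** The strongest counter-argument is that 28 is a floor. It counts dyads in which both members complete every instrument, whereas the test needs only the caregiver's own two ZBI scores. Caregivers are to be assessed however many sessions they attend, and Sections 6.1.4 and 8.1 ask people who withdraw to complete the final evaluation. If members of a dyad were lost independently and at equal rates (an illustration, not a plan figure), 28/32 complete dyads would imply 32 × √0.875 = 29.9 caregivers. At 30 pairs power is 75.4%, just inside the stated range. This stands as a reason not to treat 28 as certain. It does not justify 32, which requires no caregiver loss at all, and the plan does not state the expected number.

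Second, 32 may be meant as the intention-to-treat set with imputation. Keeping 32 people in the analysis does not restore the information of 32 pairs, as the imputation check shows, and the plan names no auxiliary variable that would recover more.

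Third, 36 recruited less 10–15% is 30.6–32.4, so 32 may already be net of one round of withdrawal. Section 9.2 nevertheless places the fall to 28 after those 32 have joined. The additional cohorts allowed in Section 8.1 apply only if withdrawal exceeds expectation.

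Fourth, a normal approximation gives 75.4% at 28 pairs. The planned test is a t-test with 27 degrees of freedom, so the t-based figure applies. The approximation also gives 80.7% at 32, so the fall of 5 to 6 points remains.

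Finally, the calculation is correct for the n it uses, the sample size was set by practical capacity, and the ZBI analysis is exploratory. All of that is true and limits the weight of the point.

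**Conclusion.** The concern holds, and it is minor. The power statement is right for 32 pairs but is not what the design delivers under the loss that the same section expects. At effect size 0.5, power is about 72% if 28 caregivers supply both ZBI scores, about 75% if 30 do, and 78% only if all 32 do.

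The 72% rests on a two-sided 0.05 paired t-test and on the stated effect size read as mean change over SD of change; both readings reproduce the plan's own range. It does not depend on the unstated ZBI SD, which matters only for translating the effect into points. The primary outcomes, feasibility and acceptability, are unaffected, and no analysis or decision rule changes.

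**What to change.** In Section 9.2, state how many caregivers are expected to have both ZBI measurements, and give power or the detectable effect for that number. If the number is 28, suitable wording would be:

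> With 28 expected pre-post pairs, power is about 72% at effect size 0.5 (69–74% over the effect sizes giving 75–80% with 32 pairs); the effect size detectable with 80% power is about 0.55.

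If more caregiver pairs than complete dyads are expected, give that number and its power instead (30 pairs: about 75% at 0.5, detectable effect 0.53). Stating the sidedness of the test and the ZBI SD in the same place would let a reader check the 3.3–4.2 point difference.

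The cost is one or two sentences and a slightly less favourable power figure. No extra participants are needed and the analysis does not change.
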